ENDPOINTS:	
EFFICACY
 
 1. Behavioral improvement with the validated scales for autistic spectrum disorders 2. Examination by child psychologist 
SAFETY
 
 1. Adverse events, especially frequency and intensity of agitation episodes 2. Modification of vital signs: blood pressure, heart rate, respiratory rate, body temperature. 3. Modification of laboratory tests: Haematology: RBC, MCHC, MCH, MCV, RDW, Hct, Hb, WBC Differential count –lymphocytes monocytes, neutrophils, eosinophils, basophils; CD45+; blood cultures Biochemistry: Serum - Bilirubin (total) AST, ALT, LDH, glucose, urea, creatinine, sodium, potassium, chloride, calcium., MB microbiology; IP – Inflammatory panel
SAMPLE SIZE:	at least 25 patients, optimum 40 patients enrolled
STATISTICAL ANALYSIS:	Summary statistics will describe the safety variables. Significance testing will be done using analysis of variance for continuous and chi-square test for categorical variables. ($\alpha = 0,05$)

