2 STUDY OBJECTIVES

The primary objective of this study is to investigate the comparative efficacy of the UCB infusion and the non-invasive treatments for improving the functioning of children with ASD.

A secondary objective is to determine whether there are significant differences in the safety profiles of the two treatments administered

In addition there will be an evaluation of the structural changes in the CNS of the children with ASD, done by MRI

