3 STUDY PLAN AND PROCEDURES

3.1 Study design

This is a twelve months long, open-label, crossover study to evaluate the comparative efficacy and safety of UCB versus non-invasive treatments in children with ASD. Each participant will receive both treatments in a random sequence.

The UCB is autologous, previously harvested at the child's birth and cryopreserved in liquid nitrogen for later use.

The UCB infusion was performed at Angiomedica Hospital, [name] as main site and in two additional clinical sites: Medicover Hospital, [name], and Ponderas Academic Hospital, [name], all in Bucharest, Romania by anesthesiologist and pediatric physician, based on the Duke protocol.

Prior to UCB infusion, HLA typing of the child will be performed at the National Institute of Hematology, as well as the HLA typing of the UCB prior to thawing – for positive identification. During this time the UCB collection will be kept in liquid nitrogen for a maximum of 72 hours, after which thawing and preparing of the UCB for infusion will be performed by [name]; the thawing is done in optimal conditions for preserving simultaneously both sterility and viability of the cryogenated cells - the Vita 34 or Rubinstein protocols; testing for viability will be done with Trypan Blue and flowcytometry. Choosing optimal conditions is based upon the minimum number of processing steps necessary (fewest number of centrifugations and shortest time of processing, with best recovery of various stem cells) and ensuring sterility.

The non-invasive treatment combination is prescribed by the study investigator after the three questionnaires are answered and an evaluation by child therapist/psychologist is performed independently. This treatment is

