5 STATISTICAL METHODS

5.1 Determination of sample size

Based on literature we expect that a sample size of minimum 25 participants will be needed in order to observe an alpha value of 0.05 (95% probability) with a p value of 0.05 and a power of 80%. ANOVA testing will be performed on the respective groups of patients

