5.2 Statistical analysis

A single statistical analysis will be performed at the end of the study. An intention to treat (ITT) approach will followed, i.e. statistical analysis of safety will be based on data from all patients and from whom meaningful data were collected. Data will be displayed graphically for visual inspection. Descriptive statistics will be presented as means, SEM and ninety percent confidence levels of the means.

Baseline characteristics. The subject disposition will be summarized. Protocol violations will be listed per subject, describing the nature of the violation. Subjects failing to complete the study (as well as the times and reasons for discontinuation) will be displayed. The demographic, background and baseline data will be presented descriptively.

Analysis of Safety. Adverse Events, as reported throughout the course of the trial will be listed individually, per treatment group. Pre-, study and post-study findings of **physical examination, vital sign variables, laboratory variables** (haematology, clinical chemistry and urinalysis), and 12-lead ECG if needed will be listed individually and summarized; values outside the normal range will be listed.

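### The only categorical test named is a chi-square test, but every child receives both treatments: the plan should name a paired test for adverse events and say whether safety is tested or described

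*Combined protocol and SAP*

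**What the plan says.** - **Design (Section 3.1):** "Each participant will receive both treatments in a random sequence". Section 3.2 continues recruitment until at least 25 children have had both.
- **Objective (Section 2):** "A secondary objective is to determine whether there are significant differences in the safety profiles of the two treatments administered".
- **Synopsis, Statistical analysis:** first "Summary statistics will describe the safety variables", then "Significance testing will be done using analysis of variance for continuous and chi-square test for categorical variables", at alpha 0.05. The second sentence does not say which endpoints it covers.
- **Section 5.1:** "ANOVA testing will be performed on the respective groups of patients".
- **Section 5.2, Analysis of Safety:** "Adverse Events, as reported throughout the course of the trial will be listed individually, per treatment group". Examination, vital-sign and laboratory findings are listed and summarised. No test is named, and the only interval in the section is a 90% one for means.

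No section mentions a McNemar test, a within-child model, or a period or sequence term. None states the counting unit for adverse events or sets a safety margin.

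**The concern.** An ordinary chi-square test assumes that the two columns of the table hold different, independent children. Here they hold the same children twice. If a child who has an event under one treatment is more likely to have one under the other, the test overstates the variance of the difference. It then rejects too seldom when there is no difference and can miss a real one. The question is a safety comparison of an infusion with a multi-component regimen in children aged 3 to 7, so a lost signal is the costly error.

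The efficacy endpoint is a difference in questionnaire scores, which is quantitative. Adverse events are therefore the obvious data for the categorical test. If the test is not meant for them, the secondary objective asks for a significance answer that no part of the plan supplies.

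**Working it through.** **The plan's own figure.** Section 5.1 states that "a sample size of minimum 25 participants will be needed" at alpha 0.05 and 80% power. It gives no endpoint, effect size, standard deviation or event rate, so the figure cannot be reproduced. Back-solving, 25 pairs detect (1.960 + 0.842)/√25 = 0.56 standard deviations of the within-child difference. Nothing ties this to safety.

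**Inputs.** From the documents: 25 pairs (optimum 40) and alpha 0.05, taken as two-sided. Assumed, because the documents give none: event rates of 5% to 60% and within-child correlation ρ from -0.2 to 0.7. Each child gives one yes/no record per treatment.

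**Set-up.** With rates pA and pB, the chance of an event under both treatments is pA·pB + ρ√[pA(1-pA)pB(1-pB)]. The other three cells follow by subtraction. All tables for 25 pairs were enumerated with their multinomial probabilities, and each test was applied to each table. For b and c discordant children, m = b + c and k = min(b, c), the mid-P McNemar value is 2·P(X ≤ k) - P(X = k), with X binomial (m, ½).

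**Type I error of the ordinary chi-square.** For equal rates p, the true variance of the difference is 2p(1-p)(1-ρ)/n, but the test uses about 2p(1-p)/n. The approximate type I error is therefore 2[1 - Φ(1.96/√(1-ρ))].

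| Rate in both periods | ρ | Approximation | Exact, 25 pairs |
|---|---|---|---|
| 30% | -0.2 | 7.4% | 7.7% |
| 30% | 0 | 5.0% | 5.4% |
| 30% | 0.3 | 1.9% | 2.2% |
| 30% | 0.5 | 0.6% | 0.8% |
| 30% | 0.7 | 0.03% | 0.1% |
| 40% | 0.39 | 1.2% | 1.7% |

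At zero correlation there is a small excess from discreteness (5.4% here, 6.5% at 50% rates). It is not an effect of pairing.

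**Power, 25 pairs.**

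| Rates | ρ | Chi-square | Mid-P McNemar |
|---|---|---|---|
| 60% v 35% | 0 | 48% | 39% |
| 60% v 35% | 0.1 | 47% | 43% |
| 60% v 35% | 0.2 | 47% | 47% |
| 60% v 35% | 0.53 | 45% | 70% |
| 50% v 20% | 0 | 64% | 58% |
| 50% v 20% | 0.46 | 68% | 87% |
| 40% v 20% | 0.3 | 32% | 40% |

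For the last row the fully exact McNemar test has 29%, less than chi-square. That is why mid-P is preferred.

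**Counting unit.** The synopsis singles out how often agitation episodes occur. If episodes are counted as independent records, the direction can change. In simulation with four records per child per treatment, clustering within child and period gave a type I error of 10% to 17%. Clustering at child level only gave 3%.

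**Precision.** With 20% in both periods, the 95% half-width for the difference is 1.96√[2(0.2)(0.8)(1-ρ)/25]: 22 percentage points at ρ = 0 and 16 at ρ = 0.5. Zero events in 25 children leaves an exact two-sided upper limit of 1 - 0.025^(1/25) = 13.7%. In 40 children it is 8.8%.

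**The case against.** **The text never says unpaired.** This is correct, and McNemar's test is itself a chi-square test. Strictly, the test is unspecified. The independent-groups reading is the natural one, because Section 5.1 speaks of groups of patients and Section 5.2 of listing per treatment group. Under either reading the remedy is to name the test.

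**Safety may be descriptive only.** The synopsis sentence on summary statistics and Section 5.2 support this, and in a pilot of this size the individual listings carry much of the weight. But Section 2 asks for significant differences, so the conflict stands.

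**The power gain depends on assumed correlation.** This also stands. One infusion and six weeks of daily agents may produce only weakly correlated events. Near zero correlation, mid-P McNemar has somewhat less power than chi-square.

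**Stronger readings that do not hold.** A reader might infer that chi-square errs in both directions and is too liberal for rare events. With 25 pairs and zero correlation its type I error is 2.0% at 5% rates and 4.9% at 10%, and positive correlation lowers it further. Events in 5 of 25 v 0 of 25 give chi-square p = 0.018 and exact McNemar p = 2(0.5)^5 = 0.063, but mid-P is 0.0625 - 0.03125 = 0.031, also significant. With 4 v 0 the tests do disagree (0.037 v 0.063), but one table is not an error rate.

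A reader might also infer that the sponsor will take non-significance as equal safety. No section says so. The low precision makes a clarifying sentence worthwhile, but the misreading is a possibility, not a plan.

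**Conclusion.** The concern holds as a gap in specification and a mismatch with the design. The data are paired, no paired method is named, and the sections disagree on whether safety is tested at all. If the named test is run in its ordinary form with one record per child per treatment, it is conservative under positive within-child correlation and loses power at moderate correlation. It is materially anti-conservative only if the correlation is negative or if repeated episodes are treated as independent.

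The sizes rest on assumed event rates and correlations, since the documents give neither. The mismatch between the test and the crossover does not depend on them. Pairing alone does not cure low power at 25 children, so intervals matter as much as the choice of test. The change should be made, but the point does not show that the trial's safety conclusions would be wrong.

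**What to change.** 1. **Synopsis and Section 5.2:** for adverse events, replace chi-square by a mid-P McNemar test on whether each child had any event in the treatment period under A and under B.
2. **Attribution:** define the periods as V1 to V2 and V2 to V3, and list later events separately. Both windows are 8 weeks, which matches the maximum for which Section 3.3.1 regards each treatment as active. Children with only one period enter the rate tables but not the paired test.
3. **Estimates:** report the paired risk difference with a 95% confidence interval, and exact 95% limits for each event rate, including zero counts.
4. **Reconcile** the synopsis, Section 2 and Section 5.2 on whether safety is tested or described, and state that a non-significant result is not evidence of equal safety.

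**Cost:** wording in three places plus the attribution rule. No new data are needed, because Section 4.4.1 already records events at every visit with onset dates. The downside is some loss of power against chi-square if within-child correlation is near zero.

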1. INTRODUCTION

1.1 Abstract

1. The treatment of children with autistic spectrum disease (ASD) represents a serious challenge for both the patients and their families, and also the medical staff involved.

Recently (Dawson G, 2017) prof Geraldine Dawson from Duke University showed that the use of stem cells from autologous umbilical cord blood (UCB) is a safe and efficacious therapy, opening a new and exciting avenue for therapeutic redress in children with ASD. This new therapeutic venue has yielded more dramatic improvements than any previous treatment including intranasal oxytocin.

We know that ASD has multiple determinants - genetic, environmental, neurological, and immunological (Young 2016) – and the pathological processes involved in ASD are various and complex. ASD is after all a spectrum of diseases involving brain development, not just a well-defined condition, and the implication is that the one-molecule-fits-all type of treatment will not be likely to address the multitude of aspects and deficiencies which are present in individuals with ASD. UCB itself contains a plethora of molecules which can modulate the activities of neurons and the supporting microglia, so comparing it with just one therapeutic substance would not be a good strategy.

With this in mind, we propose that ASD treatment should be very much personalized after a careful evaluation of the patient, and a noninvasive treatment option should include two or more substances from the following: oxytocin, curcumin, magnesium citrate with vitamin B6, pironoquinolinquinone (PQQ), lecithin, piracetam, and optionally dimethylfumarate, a medication known to be both neuroprotective and immunomodulatory.

Below we propose a pilot clinical study which aims to compare the safety and efficacy of UCB administration versus a less invasive and costly therapeutic option which consists of a patient-specific combination of medications and supplements. The study will be open-label, crossover type, meaning that all children will get sequentially both treatments after a 2-week washout interval. This study design has the advantage of eliminating the ethically questionable administration of a placebo.

1.2 Background

There is ample information in the medical literature on ASD, due to the increasing incidence of the condition, impact on families and society and the healthcare costs associated with it. As it affects the neuropsychological status of the developing child, it is classified and studied as a psychiatric ailment, and as such DSM-5, characterizes ASD behavior by the following traits:

- difficulties in social reciprocity and communication,
- unusually narrow interests,
- repetitive behaviours and speech,
- insistence on sameness, and
- idiosyncratic sensory responses

We also know that genetic, environmental, neurological, and immunological factors contribute to its etiology and among these we mention:

- increased rate of amygdala growth (Nordahl, 2012)
- atypical pruning of synapses (Geschwind 2007)
- decreased connectivity between ventromedial prefrontal cortex, which is implicated in emotion and social communication and the middle temporal gyrus/superior temporal sulcus region, which is implicated in face expression processing involved in social behaviour; also the precuneus/superior parietal lobule region with reduced functional connectivity, which is implicated in spatial functions including of oneself, and of the spatial environment (Xydakis 2015)
- neuron density in the prefrontal cortex was shown to play a significant role (Courchesne 2011)
- neuroinflammation in the anterior areas of the cortex (Pardo, 2005;
- increased head size in ASD children correlated with a history of allergic/immune disorders, (Sacco, 2007, Nordahl, 2011)
- increased titers of maternal autoimmune antibodies (Croen 2008, Braunschweig 2012)

Considering all the above, the consensus is that the prevailing pathological modification in children with ASD is the presence of a persistent pro-inflammatory status in the central nervous system (CNS) of the patient (Young 2016).

There are not many treatment options which are known to be effective in treating ASD. Secretin, oxytocin (Parker 2017), vaccines were among the treatments studied, but the results of the respective clinical studies were not at all encouraging.

1.2 Study Rationale

Even though it is a recent development, UCB has had the best results so far in treating children with ASD and its results recommend it for treatment to any child with ASD and who had UCB collected at birth. Two important questions arise:

- what other treatment can be recommended to the ASD children without UCB collected at birth, and with what comparative efficacy, and
- being a one-time intervention, can we improve/add to UCB infusion other substances which have a very good safety profile (well tolerated) and at least theoretically have a benefit in improving neuronal function?

To begin to answer these questions we have devised an open-label clinical study with a crossover design (all children receive both treatments, albeit in a different sequence).

One important novelty with our study is that the treatment to which UCB is compared is not the same to all children, but is individually tailored to address specifically the most important problems the child has (inflammation, anxiety/social avoidance, myelination, global delay, etc)

Based on the results of the testing with the M-CHAT-R, Q-CHAT and CAST questionnaires and the evaluation from child psychologist, a recommendation for treatment will be made.

The noninvasive treatment consists of a combination of at least two substances from the

following: Oxytocin 10 UI/day intranasally, Magnesium citrate and vitamin B6 ½ cp qd, pironoquinolinquinone (PQQ) 20 mg qd, Lecithin 1000 mg qd, Curcumin 500 mg qd. The specific treatment components will be recommended and administered according to the criteria below, after performing all the tests (imagistics, labs, questionnaires) which can suggest a deficiency on one or more of the following directions:

- inflammatory problem (IP markers on labs, white matter changes, diffuse or no specific modification on MRI)
- myelination (MRI changes),
- anxiety/social avoidance (questionnaires),
- severe developmental delays in cognition, logic, verbalization

1. ***Curcumin 250 mg bid*** will be included in the child's regimen if the imagistics (MRI/CT scan) and/or laboratory values (IP) suggest the presence of an inflammatory status, either in the CNS (white matter modifications on the brain scan) or systemic (abnormal values in the Inflammatory Panel done from blood);

2. ***Oxytocin 10 UI/day*** via intranasal administration will be administered if a social-communication deficit is clearly shown at evaluation

3. ***Lecithin 500 mg bid*** will be administered if brain imaging reveals any demyelination/myelination deficits, global cerebral atrophy or regional atrophy

4. ***Magnesium citrate with vitamin B6 (150 mg/6 mg qd)*** will be included if restlessness/agitation/anxiety is present significantly in the clinical picture

5. ***Piranoquinolinquinone (PQQ) 20 mg/day*** will be administered in situations of apathic/disinterested behavior, marked introversion, marked developmental delays

6. ***Optional medication for special situations***, with parent's clear understanding, a few other treatment options will be included – ex.

- Tecfidera (dimethyl fumarate) 60 mg bid with food (presence of hypo/demyelination with an autoimmune component); immune modulation is involved in ASD as documented in Kornberg, 2018
- Boswellia extract 400 mg bid – decreases activation of NfK-beta which is the main modulator of both inflammation and neuronal connections
- piracetam (Nootropil) 400 mg bid (presence of severe developmental delays with low motor coordination and energy levels)
- Bacopa monieri (presence of demyelination in absence of immune over-activation)
- Uridine (inflammation mitigation, mitochondrial function stimulation)
- Hipophae rhamnoides oil (source of omega-7 unsaturated fatty acids for synaptic vesicles)

The decision of which of these components should be given is taken after all tests are done and the child psychologist/therapist and the study investigator discuss the case and afterwards discuss the practical issues of administering the recommended treatment with the parents.

2 STUDY OBJECTIVES

The primary objective of this study is to investigate the comparative efficacy of the UCB infusion and the non-invasive treatments for improving the functioning of children with ASD.

A secondary objective is to determine whether there are significant differences in the safety profiles of the two treatments administered

In addition there will be an evaluation of the structural changes in the CNS of the children with ASD, done by MRI

3 STUDY PLAN AND PROCEDURES

3.1 Study design

This is a twelve months long, open-label, crossover study to evaluate the comparative efficacy and safety of UCB versus non-invasive treatments in children with ASD. Each participant will receive both treatments in a random sequence.

The UCB is autologous, previously harvested at the child's birth and cryopreserved in liquid nitrogen for later use.

The UCB infusion was performed at Angiomedica Hospital, [name] as main site and in two additional clinical sites: Medicover Hospital, [name], and Ponderas Academic Hospital, [name], all in Bucharest, Romania by anesthesiologist and pediatric physician, based on the Duke protocol.

Prior to UCB infusion, HLA typing of the child will be performed at the National Institute of Hematology, as well as the HLA typing of the UCB prior to thawing – for positive identification. During this time the UCB collection will be kept in liquid nitrogen for a maximum of 72 hours, after which thawing and preparing of the UCB for infusion will be performed by [name]; the thawing is done in optimal conditions for preserving simultaneously both sterility and viability of the cryogenated cells - the Vita 34 or Rubinstein protocols; testing for viability will be done with Trypan Blue and flowcytometry. Choosing optimal conditions is based upon the minimum number of processing steps necessary (fewest number of centrifugations and shortest time of processing, with best recovery of various stem cells) and ensuring sterility.

The non-invasive treatment combination is prescribed by the study investigator after the three questionnaires are answered and an evaluation by child therapist/psychologist is performed independently. This treatment is

